9.4 Recruitment rates

Stage 1 (Work Package 1)

For surveys, we aim to recruit a minimum of 150 people with learning disabilities or autistic people up to a maximum of 300. Within this we aim to recruit a minimum of 30 children aged 17 or younger, who will provide data in a manner best suited to meet their individual communication needs (including full survey, shorter version of the survey, or Talking Mats® interview). We also aim to recruit a minimum of 150 family members/carers up to a maximum of 300. We will ensure the sample includes key sub-groups: children and young people, adults, those who are at risk of admission to hospital, and those currently within different hospital settings (e.g., acute ward, inpatient forensic services, psychiatric intensive care unit, specialist inpatient mental health services).

Running in parallel with the surveys, we will complete structured interviews with a minimum of 25 people with learning disabilities and autistic people who have moderate to severe learning disabilities, including children and adolescents with moderate to severe learning disabilities. These participants will be in addition to the minimum of 150 people with learning disabilities or autistic people who will complete the surveys.

Stage 1 (Work Package 2)

A minimum of 350 C(E)TR panel members, including EbE and health and social care professionals involved in C(E)TRs will be surveyed. A minimum of 200 C(E)TR panel members (Chairs, Independent Clinical Members, and EbE) up to a maximum of 400, and a minimum of 150 health and social care professionals (commissioners, social workers, advocates, paid and unpaid care staff, clinical staff psychiatrists, nurses, psychologists, allied health professions) up to a maximum of 300 will be recruited.

Stage 2 (Work Package 3)

Overall, 20 case over time. Within this, 10 adults and 10 children.

Stage 3 (Work Package 4)

Combining both datasets, we anticipate having data for 132 months (11 years).

Stage 4 (Work Package 5)

N/A

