13.1 Sample size

Stage 1 (Work Package 1)

A minimum of 150 people with learning disabilities and autistic people (inclusive of 30 children and young people), and a minimum of 150 carers and/or family members will complete the survey or Talking Mat[®]; this sample size is considered sufficient to allow for the capture of the diversity of experiences and voices from different people with learning disabilities, autistic people, and their carers and family members. The additional 25 Talking Mats[®] interviews will supplement the survey

CECILIA protocol v1.1 27.02.2025

Autistic

data with direct experiences from children and adults with more severe learning disabilities. Assuming a sample size of 150, if 50% of respondents endorse our outcomes in one direction (e.g., satisfied with C(E)TRs, agree that C(E)TRs improved care pathways) then the 95% CI would cover a range [42%, 58%] that will give a good degree of precision for interpretation in terms of meaning for practice and policy.

Stage 1 (Work Package 2)

A minimum of 350 participants was considered sufficient to allow for the capture of enough data to reflect the diversity of experiences and voices amongst C(E)TR panel members, and health and social care professionals. Based upon a sample size of 350, if we consider 50% respondents endorse our outcomes in one direction (e.g., satisfied with C(E)TRs, agree that C(E)TRs improved care pathways) then the 95% CI would cover a range [42%, 58%] that will give a good degree of precision for interpretation in terms of meaning for practice and policy.

Stage 2 (Work Package 3)

A sample size of 20 cases has been selected to ensure we are able to identify common patterns within the data whilst also keeping the analytical process manageable in line with the planned timeframe and resources requested. Sample sizes in the development of temporal pathway models using grounded theory do tend to be relatively small given the depth of analysis required. It is generally accepted that a sample size of at least 15 participants is required to achieve saturation of the data in the development of temporal pathway models and a key strength of grounded theory is its ability for future modification in response to additional data [26-28].

Stage 3 (Work Package 4)

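### The Work Package 2 precision statement gives [42%, 58%] for 350 respondents; that interval belongs to 150 respondents, and 350 give [44.8%, 55.2%]

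*Protocol*

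**What the plan says.** Protocol section 13.1 has one precision statement for each Stage 1 survey.

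- **Work Package 1** (people with learning disabilities and autistic people; family members and carers): "Assuming a sample size of 150, if 50% of respondents endorse our outcomes in one direction", followed by the interval [42%, 58%].
- **Work Package 2** (panel members; health and social care professionals): "Based upon a sample size of 350, if we consider 50% respondents endorse our outcomes in one direction", followed by the same interval.

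Both paragraphs end in the same words: "then the 95% CI would cover a range [42%, 58%] that will give a good degree of precision".

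The Work Package 2 paragraph opens with a qualitative reason for the number: "A minimum of 350 participants was considered sufficient to allow for the capture of enough data". Section 9.4 and the synopsis split the 350 into two recruitment quotas. The first reads "A minimum of 200 C(E)TR panel members (Chairs, Independent Clinical Members, and EbE) up to a maximum of 400". The second quota is for professionals, with a floor of 150 and a ceiling of 300.

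**The concern.** With the proportion and the confidence level fixed, the width of the interval depends only on the number of respondents. Two surveys of 150 and 350 cannot share one interval, so at least one of the two statements must be wrong.

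The interval is the only quantitative support for the Work Package 2 sample size, and the protocol rests on it the claim that precision is good enough to inform practice and policy. If the interval is wrong, that claim describes a survey of a different size from the one planned. The figure could also be carried into later documents, such as the analysis plan or the final report.

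**Working it through.** **Inputs, all from the protocol**

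- Proportion endorsing: p = 0.50 (section 13.1, both paragraphs)
- Confidence level: 95%, so z = 1.96 (section 13.1)
- Work Package 1: n = 150 (section 13.1)
- Work Package 2: n = 350 in total (section 13.1), with minimum quotas of 200 panel members and 150 professionals (section 9.4 and synopsis)

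**Formula**

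Half-width = z × √(p(1 − p)/n) = 1.96 × √(0.25/n)

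**Step 1. Reproduce the Work Package 1 figure.** For n = 150: 1.96 × √(0.25/150) = 1.96 × 0.04082 = 0.0800. The interval is 42.0% to 58.0%, as the protocol states.

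**Step 2. Apply the same formula to Work Package 2.** For n = 350: 1.96 × √(0.25/350) = 1.96 × 0.02673 = 0.0524. The interval is 44.76% to 55.24%. The stated [42%, 58%] is not reproduced.

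**Step 3. Try other interval methods at n = 350.**

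| Method | Interval |
|---|---|
| Wald | 44.76% to 55.24% |
| Wald with continuity correction | 44.62% to 55.38% |
| Wilson | 44.79% to 55.21% |
| Agresti-Coull | 44.79% to 55.21% |
| Clopper-Pearson exact | 44.64% to 55.36% |
| Wald at 99% confidence | 43.12% to 56.88% |

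None gives [42%, 58%], not even at 99% confidence.

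**Step 4. Ask what would give an 8-point half-width.** Solving for n: 0.25 × (1.96/0.08)² = 150.06. Rounding does not help: half-widths of 7.5 and 8.5 points correspond to about 171 and 133 respondents, both far from 350. Keeping 350 respondents would need a design effect of 350/150.06 = 2.33. Section 13.1 mentions no design effect, clustering or non-response allowance for this survey.

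**Step 5. Size of the discrepancy.** 8.00/5.24 = 1.53, so the stated interval is about 53% too wide. It describes a survey with 150/350 = 43% of the planned respondents.

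**Step 6. The two quotas.** For 200 panel members: 1.96 × √(0.25/200) = 0.0693, giving 43.1% to 56.9%. For 150 professionals the result is that of step 1, 42.0% to 58.0%.

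**The case against.** The arithmetic is hard to dispute; the case on the other side is about weight and cause.

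- **The error is conservative.** True precision at 350 is better than stated. The protocol already regards ±8 points as good, so its conclusion holds more strongly after correction. The Work Package 2 analysis in section 14 consists of descriptive summaries, content analysis and costing of exemplars; no test, power claim or decision threshold depends on the interval. This stands, and it limits the consequence: the design is not harmed.
- **The interval is not the only justification.** The paragraph first appeals to diversity of experience, and 350 is a minimum, so the achieved precision may differ. This also stands, but the interval remains the only number offered.
- **The cause is not known.** The figure may have been carried over from Work Package 1. It may instead have been meant for the 150 professionals, for whom [42%, 58%] is right; the wrong element would then be the 350. The documents do not settle this. On either reading the sentence pairs an interval with a sample size that does not produce it, and on the second it also leaves out the panel members.
- **Section 13.1 claims no precision for the two groups separately.** This is correct. The group intervals are a useful addition; only the mismatch between 350 and [42%, 58%] is an error.

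**Conclusion.** The concern holds. At 50% endorsement and 95% confidence, 350 respondents give [44.8%, 55.2%], a half-width of 5.24 points against the 8.0 points stated. The printed interval fits 150 respondents. The Work Package 1 statement is correct and needs no change.

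The result assumes simple random sampling with no design effect, as the protocol's own Work Package 1 figure does, and it does not depend on the choice of interval method. The error understates precision, so the target of 350 remains adequate by the protocol's own standard. It should still be corrected, because it is a demonstrably wrong figure in the sample-size justification and contradicts the paragraph directly before it.

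**What to change.** In section 13.1, Stage 1 (Work Package 2), replace the interval so that 350 respondents with 50% endorsement have a 95% CI of about [45%, 55%] (44.8% to 55.2%).

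Preferably add the intervals at the two quota minima: about [43%, 57%] for 200 panel members and [42%, 58%] for 150 health and social care professionals. This tells the reader what precision to expect if the groups are reported separately, and it covers the case in which the interval for the 150 was the one intended.

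The cost is one sentence. Recruitment targets, analysis and budget are unchanged.

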BIRMINGHAM

Jniversity of

The Public Accounts Committee [9] stated that C(E)TRs are the main mechanism for reducing the number of people in hospital and expressed concern that they were not working as intended. C(E)TRs are undertaken by an independent panel comprised of an Expert by Experience (EbE), a clinician, and the commissioner who chairs the meeting and is also responsible for funding an individual's care. The autistic person or the person with learning disability and their family also attend the meeting. C(E)TRs can take place in the community with someone who is identified as at risk of admission to hospital, or in hospital, after someone has been admitted. After admission, C(E)TRs initially take place within six weeks, and then take place every three months for children, every six months for adults within non-secure services, and every twelve months for adults in secure services. However, C(E)TRs can be requested at any time by an individual, their family, the commissioner, an advocate, or the clinicians supporting the person. For those in the community at risk of admission, the primary aim of a community C(E)TR is to undertake a review of care to determine whether a person's needs could be better met in a community setting, as opposed to hospital, with additional support. Admission to hospital should be a last resort and only happen when remaining in the community will place the individual and others at significant risk of harm. For those who are admitted, the focus of a C(E)TR is to determine whether someone needs to remain in hospital for continuing care, and to identify barriers to discharge and develop solutions to these barriers.

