5.3 Research questions

UNIVERSITYOF

BIRMINGHAM

INHS

Coventry and Warwickshire Partnership

- 1. What are the experiences of people with learning disabilities and autistic people, families, C(E)TR panel members and a range of health and social care professionals when taking part in C(E)TRs?
- 2. How are experts by experience being included and supported to take part in C(E)TRs? What are the barriers and facilitators to participation and how can their participation be promoted?
- 3. How are C(E)TRs being carried out in practice with different groups (e.g., children, adults, autistic adults without learning disabilities) and in different settings (e.g., assessment and treatment units, secure units, acute mental health wards, inpatient units for children)?
- 4. What impact do C(E)TRs have upon care-pathways, and how are recommendations and outcomes implemented and monitored?
- 5. What barriers and facilitators to discharge are identified by C(E)TRs and how are they overcome or addressed by care teams?
- 6. How are C(E)TRs different, similar to, or integrated with existing methods for reviewing care (e.g., Care Programme Approach, Child Protection Conferences, Extraordinary Care Review Meetings)?
- 7. How are C(E)TRs structured and managed to support inclusion, and what adjustments and supports aid participation (e.g., augmentative and alternative communication) of people with learning disabilities and autistic people, and how can these be improved?
- 8. Is there evidence that people with learning disabilities and autistic people who are receiving a C(E)TR are being empowered as a consequence of C(E)TRs? What are the barriers and facilitators to empowerment and how can this be promoted?
- 9. Is there a relationship between the skill mix of a C(E)TR panel and the recommendations or outcomes made and are they implemented and how?
- 10. Are C(E)TRs associated with reducing inpatient numbers and what effect do they have on costs?
- 11. What are likely resource implications of C(E)TR and how might they differ between different types of individuals?

6 Study design and data collection methods overview

This research has four stages comprising five work packages using mixed methods. Lived Experience Advisory Panels (LEAPs) will co-produce study materials and will be actively engaged throughout

Challenging

Behaviour

Foundation

National Autistic

BIRMINGHAM

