each stage and all work packages. Initially, we will co-develop a logic model informed by existing guidance and other literature to describe C(E)TR key activities, mechanisms of change, and outcomes which will be used to inform the choice of survey and interview questions and analysis within Stages 1 and 2, the analytic strategy within Stage 3, and the data triangulation within Stage 4. Our logic model will be developed in collaboration with our Lived Experience Advisory Panels (LEAPs) and the Study Management Group inclusive of C(E)TR panel members. We will also seek direct feedback from lead staff in NHS England who lead C(E)TR policy.

National Autistic

Within Stage 1, national surveys (co-produced with our LEAPs) will be circulated to people with learning disabilities and autistic people, including children and young people, families and carers, C(E)TR panel members, and health and social care professionals. Surveys will ask about their experiences of taking part in C(E)TRs and also gather data to inform estimates of the likely cost of undertaking C(E)TRS. We will use adapted methods, led by our expert partners and with LEAP input to capture the voice of younger children and those with moderate-severe learning disabilities and those with associated communication difficulties including children and young people whose views and experiences are often not collected.

Within Stage 2, we will attend C(E)TRs, and CPA meetings to track individual progress over time, collect naturalistic data from the meetings, and undertake semi-structured interviews with attendees. We will undertake a linguistic analysis of our data to determine the relative contributions of different individuals to the decision-making process, and we will develop a descriptive temporal pathway model of C(E)TRs process over time and determine how C(E)TRs affect care pathways.

In Stage 3, we will model relationships between C(E)TRs and numbers of admissions, discharges, total number of inpatients, types of inpatient service, consider cost-implications and length of stay over time using anonymised data available from NHS Digital for children and adults.

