Given our sample size, we will take a pragmatic approach, consulting with stakeholders and informed by the C(E)TR logic model, to determine a minimum adjustment set of potential predictors by creating a Directed Acyclic Graph (DAG) that maps out our assumptions about the causal pathways between C(E)TRs, the number of inpatients over time and additional predictors [49]. This process is designed to ensure that additional variables that may have an influence on the direct relationship (e.g., confounders, mediators, and moderators) between C(E)TRs and the number of inpatients over time are considered, and adjusted for, if required. This would likely include models determining the relationship between use of C(E)TRs and admissions, discharges, and number of inpatients over time, along with type of inpatient service (e.g., mental health, forensic, adult, child), length of stay, age, diagnosis of learning disability, autism, or both, use of advocacy, discharge location, length of stay over time and other key factors.

[figure not shown]
Information from the time-series modelling will be used to inform estimates of the potential cost implications of C(E)TRs. From Stage 1, we will have estimates of the indicative costs of C(E)TRs and how this might vary across different people. We would also have information on typical effects on care pathways, and associated costs. Using time-series modelling we aim to show the relationship between C(E)TRs, inpatient stays, and other variables. Costs can be applied to inpatient stays, potential confounding factors, and C(E)TRs themselves to explore what effects C(E)TRs might be having on NHS and care costs. If relationships are found between C(E)TRs and these predictors, then we can estimate the potential resource implications of these changes. Estimates could also be produced by different patient groups (e.g., adults compared to children). Where data indicate, we could also model 'what if' scenarios such as how much would C(E)TRs need to reduce inpatient stays to offset their cost. However, it should be noted that we do not intend to carry out an economic evaluation to determine if C(E)TRs represent a cost-effective service as we will not have patient related outcomes in terms of changes in health or other relevant outcomes related to the use of C(E)TRs in a manner that will allow for this type of analysis.

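### Stage 3 targets a direct relationship and allows adjustment for mediators, whereas research question 10 and the costing need the total effect of C(E)TRs

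*Protocol*

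**What the plan says.** Section 14 (Analysis, Stage 3, Work Package 4) plans to consult stakeholders and use the logic model "to determine a minimum adjustment set of potential predictors by creating a Directed Acyclic Graph (DAG"). The stated purpose is to take account of "additional variables that may have an influence on the direct relationship", and the sentence continues: "e.g., confounders, mediators, and moderators) between C(E)TRs and the number of inpatients over time are considered, and adjusted for, if required".

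The next sentence begins "This would likely include models determining the relationship between use of C(E)TRs and admissions, discharges, and number of inpatients over time". It then adds service type, length of stay, age and diagnosis, and ends with "use of advocacy, discharge location, length of stay over time and other key factors". Length of stay appears twice in that sentence. No item is given a role as outcome or covariate.

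Three other places bear on this:

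- Section 5.3, research question 10: "Are C(E)TRs associated with reducing inpatient numbers and what effect do they have on costs".
- Section 6, on Stage 3, places length of stay among the quantities to be modelled: "consider cost-implications and length of stay over time using anonymised data". The schema in section 3.1 does the same.
- Section 4 gives the intended mechanism. Inpatient numbers are to fall through admission avoidance and discharge, and for people already admitted a C(E)TR is meant to "identify barriers to discharge and develop solutions to these barriers".

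**The concern.** Three kinds of variable that need different handling share one rule. Confounders belong in the adjustment set. Moderators call for interaction terms. Mediators stay out of a model for the total effect and enter only when a direct effect is wanted.

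Research question 10 asks whether C(E)TRs go with lower inpatient numbers and what they do to costs. The costing applies unit costs to the modelled link between C(E)TRs and inpatient stays, including how far stays would have to fall to offset the cost of the reviews. Both uses need the whole effect, including the part that runs through discharge or a shorter stay.

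Interpretation is also at stake. Section 4 reports that the team's earlier time-series analysis found post-admission C(E)TRs associated with more discharges, but C(E)TRs unrelated to total inpatients. If Stage 3 conditions on the pathway and again finds no relation to total inpatients, the reader cannot tell a true null from one produced by the adjustment.

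**Working it through.** **The plan's own figure.** The only Stage 3 power figures (section 13.1: 84% and approaching 100%, alpha 0.05) refer to the overall trend and the number in contact with services, not to the C(E)TR coefficient. They cannot be reproduced, because the effect sizes, residual SD and autocorrelation come from a cited study and are not given. They do not bear on this point.

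**Step 1: question against target.** Research question 10 and the costing ask for the total effect. Section 14 names a direct relationship. The adjustment set read from a causal diagram depends on which effect is requested: for a total effect it excludes mediators, and for a direct effect it includes them.

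**Step 2: what conditioning does.** Let X be C(E)TR use, M a mediator and Y inpatient numbers, with M = aX + e and Y = cX + bM + u.

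- Total effect = c + ab.
- Coefficient on X with M in the model = c.
- Mediated share p = ab / (c + ab), so c = (1 - p) × total.

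With an assumed total of -0.40, c is -0.40, -0.30, -0.20, -0.10 and 0 for p = 0, 25, 50, 75 and 100%.

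**Step 3: check by simulation.** From the protocol: 11 × 12 = 132 monthly points, alpha 0.05, regression with autoregressive errors. Assumed: total effect -0.40, a = -0.5, unit SD for X and for both noise terms, autocorrelation 0.3 in X and in the mediator noise, error autocorrelation 0.5 or 0.8, AR(1) errors, 600 runs per setting. For p = 50%: b = (-0.40 × 0.5) / (-0.5) = 0.40, c = -0.20, and c + ab = -0.20 - 0.20 = -0.40.

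| Mediated share | Coefficient with mediator, AR 0.5 | Power | Coefficient with mediator, AR 0.8 | Power |
|---|---|---|---|---|
| 0% | -0.406 | 0.99 | -0.402 | 1.00 |
| 25% | -0.300 | 0.93 | -0.297 | 1.00 |
| 50% | -0.200 | 0.64 | -0.205 | 0.97 |
| 75% | -0.110 | 0.23 | -0.100 | 0.42 |
| 100% | -0.009 | 0.05 | -0.003 | 0.04 |

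Without the mediator, the coefficient stayed between -0.398 and -0.410 in all ten settings, with power from 0.97 to 1.00.

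**Step 4: paths in opposite directions.** With two mediators, total = c + a1b1 + a2b2, and conditioning on the first alone leaves c + a2b2. If a1b1 and a2b2 differ in sign, the result can lie further from zero than the total, or change sign. Section 4 gives reason to consider this: pre-admission C(E)TRs were associated with more admissions, which raise inpatient numbers, and post-admission C(E)TRs with more discharges, which lower them. Bias towards zero is therefore not assured.

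**The case against.** The best defence is that the plan already uses the right tool. The variables are to be adjusted for only if required, and a causal diagram decides. Placing mediators on such a diagram is how one learns not to condition on them, and the word *direct* may be meant loosely. The choice of estimand and the final covariate list are also commonly left to a statistical analysis plan, which is not shown.

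Much of this stands, and it rules out several stronger readings:

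- A reader might infer that Stage 3 will adjust for mediators. The text makes this conditional.
- A reader might infer that length of stay and discharge location are planned covariates. The list assigns no role, and sections 3.1 and 6 set length of stay among the quantities modelled against C(E)TRs.
- A reader might infer that the C(E)TR effect would be removed. That needs full mediation. Conditioning inpatient numbers on admissions and discharges together would come close to it, since these flows make up the change in numbers, but the protocol nowhere says it will do so.
- A reader might infer that admissions and length of stay must never be adjusted for. Section 4 ties reviews to the time since admission, with intervals that depend on age group and security level. Earlier admissions and time already in hospital therefore affect both how many reviews fall due and how many people are inpatients, and can be confounders.

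The defence does not remove the mismatch. If *direct* is meant technically, the diagram calls for mediators to be included. If it is meant loosely, naming mediators in the adjustment sentence contradicts the total-effect set. The protocol states a target and a rule here, so this is more than detail left for later.

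**Conclusion.** The adjustment target as written does not match research question 10 or the costing. A model that conditions on variables downstream of a C(E)TR would distort the total effect. When the paths act in the same direction, the loss equals the mediated share: a quarter of the effect at 25%, half at 50%, all of it only at 100%. When they oppose each other, the coefficient can move either way.

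The proportional result holds for a linear model in which nothing unmeasured drives both mediator and outcome. The power figures rest on the assumed effect of -0.40 and the assumed autocorrelations. The documents give neither the mediated share nor an expected C(E)TR effect, so the size in this study is unknown.

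This is an error of wording with a real analytic consequence if followed literally. It is not an announced analysis that erases the effect. It should be corrected, but because adjustment is conditional and the diagram has still to be drawn, it does not rank among the changes without which the study could not proceed.

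**What to change.** Amend the Stage 3 text in section 14 as follows:

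1. State that the total effect of C(E)TRs on inpatient numbers is the target for research question 10 and for the costing.
2. Take the minimum adjustment set from the causal diagram for that effect, so that it holds confounders only. These may include values from before the C(E)TR, such as lagged admissions or time already in hospital.
3. Delete *mediators* from the adjustment sentence and handle moderators as interactions.
4. Give each listed variable a role. Model admissions, discharges, length of stay and discharge location that follow the C(E)TR as separate outcomes.
5. Label any model that includes mediators as a separate direct-effect analysis, and do not use it for research question 10 or the costing.

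The cost is a few sentences in the protocol or the statistical analysis plan. No new data are needed. The change should be in place before the Stage 3 work scheduled for months 21 to 27 (section 3.2).
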